## 6. DATA CONVENTIONS

The following analysis conventions will be used in the statistical analysis.

### 6.1. Definition of Baseline for Efficacy/Safety Variables

Unless otherwise specified, the baseline assessment of the study for all measurements will be the latest available valid measurement taken prior to the first administration of study drug. If any randomized patients are not treated, the baseline will be the last value on or prior to the randomization. The baseline of worst scratch/itch scale is defined in Section 4.4.2.

The following rules specify the determination of baseline by both date/time information:

1. For the AE, lab, PK and ADA data, both date and time of the measurement will be used to determine baseline by comparing with the first injection date and time.
2. For other data except AE, lab, PK or ADA, only date of the measurement will be used to determine baseline by comparing with the first injection date.

For the rescreened patients, all data from the same patient will be used to derive baseline regardless if the data is from the screen- failure subject ID or enrolled subject ID.

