6.2.3. Safety Procedures

6.2.3.1. Vital Signs

Vital signs (including sitting systolic and diastolic blood pressure, heart rate, respiration, and temperature) will be collected pre-dose at every in-clinic visit.

During part A, at the baseline visit, patients will be monitored at the study site for a minimum of 2 hours after study drug administration. Vital signs (systolic and diastolic blood pressure, heart rate, respiration, and temperature) and AE assessments will be performed at 30 minutes (± 10 minutes) post-injection and then at 2 hours (± 15 minutes) post-injection. See Section [6.1](#), [Table 1](#) (Part A), for assessment time points.

During part B, patients will be monitored at the study site at certain dosing visits for a minimum of 2 hours after study drug administration. Vital signs (systolic and diastolic blood pressure, heart rate, respiration, and temperature) and AE assessments will be performed at 30 minutes (± 10 minutes) post-injection, and at 2 hours (± 15 minutes) post-injection. See Section [6.1](#), [Table 2](#) (Part B), for assessment time points.

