9.6. Additional Statistical Data Handling Conventions

The following analysis and data conventions will be followed:

Definition of baseline:

- The baseline assessment in part A will be the latest valid, pre-first-dose assessment available in part A
- The baseline assessment in part B will be the latest valid, pre-first-dose assessment available in part B

General rules for handling missing data:

- Rules for handling missing data for efficacy assessments are provided in Section 9.5.2.
- If the start date of an AE or concomitant medication is incomplete or missing, it will be assumed to have occurred on or after the intake of study medication, except if an incomplete date (eg, month and year) clearly indicates that the event started prior to treatment. If the partial date indicates the same month or year of the intake of study medication date, then the start date by the study medication intake date will be imputed, otherwise, the missing day or month by the first day or the first month will be imputed.
- No imputations for missing laboratory data, ECG data, vital sign data, or physical examination data will be made.

Visit windows:

- Assessments taken outside of protocol allowable windows will be displayed according to the CRF assessment recorded by the investigator.

Unscheduled assessments:

- Extra assessments (laboratory data or vital signs associated with non-protocol clinical visits or obtained in the course of investigating or managing AEs) will be included in listings, but not summaries. If more than 1 laboratory value is available for a given visit, the first observation will be used in summaries and all observations will be presented in listings.

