**Figure 1: Overall Design**

The Part A of AD-1539 has been completed. The CSR has been finalized and approved in Dec 2020. This document focuses on Part B of the study only.

AD-1539 B is a randomized, double-blind, placebo-controlled, parallel-group study to investigate the efficacy and safety of SC dupilumab when administered concomitantly with TCS in pediatric patients,  $\geq 6$  months to  $< 6$  years of age, with moderate-to-severe AD. Approximately 160 patients are planned to be randomized in the study. The number of patients with moderate AD (IGA=3) is capped at approximately 40 patients. Figure 1 shows the overall design of AD-1539 (Parts A and B).

[figure not shown]
Part B consists of the following 3 periods: a screening period of up to 56 days (including 2 weeks of TCS standardization), a treatment period of 16 weeks, and a follow-up period of 12 weeks (Figure 3). Patients who enrolled in Part A of the study are not eligible to participate in Part B.

Patients who continue to meet eligibility criteria at baseline undergo day 1/baseline assessments. Patients are randomized in a 1:1 ratio stratified by baseline body weight ( $\geq 5$ - $< 15$  kg and  $\geq 15$ - $< 30$  kg), baseline disease severity (IGA=3 and 4), and region/country (North America and Europe). Approximately 160 patients are randomized to 1 of the following 2 treatment regimens (Figure 2):

- dupilumab Q4W tiered fixed-dose (200 mg or 300 mg) treatment regimen:
  - Patients with baseline weight  $\geq 5$  to  $< 15$  kg receive an SC injection of 200 mg dupilumab (1.14 mL of a 175 mg/mL solution) on day 1 and then 200 mg Q4W from week 4 to week 12.
  - Patients with baseline weight  $\geq 15$  to  $< 30$  kg receive an SC injection of 300 mg dupilumab (2 mL of a 150 mg/mL solution) on day 1 and then 300 mg Q4W from week 4 to week 12.
- placebo Q4W treatment regimen: patients receive matching placebo on day 1 and then Q4W from week 4 to week 12.
  - In the  $\geq 5$  to  $< 15$  kg weight stratum, patients randomized to placebo receive Q4W injections of placebo (1.14 mL) matching 200 mg dupilumab.

- In the  $\geq 15$  to  $< 30$  kg weight stratum, patients randomized to the placebo group receive Q4W SC injections of placebo (2 mL) matching 300 mg dupilumab.

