#### **4.5.3. Vital Sign Variables**

The following vital signs parameters will be collected:

- Respiratory rate (bpm)
- Heart rate (beats/min)
- Sitting systolic and diastolic blood pressures (mmHg)
- Body temperature (°C)

Patients will be monitored at the study site at certain dosing visits for a minimum of 2 hours after study drug administration. Vital signs (systolic and diastolic blood pressure, heart rate, respiration, and temperature) will be performed at 30 minutes ( $\pm 10$  minutes) and 2 hours ( $\pm 15$  minutes) post-injection. See [Appendix 3](#) for assessment time points.

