## **5.7. Analysis of Safety Data**

The analysis of safety and tolerability will be performed based on the SAF.

The safety analysis will be based on the reported AEs, clinical laboratory evaluations, physical examination, vital signs and 12-lead ECG.

Thresholds for treatment-emergent Potentially Clinically Significant Values (PCSVs) in laboratory variables and vital signs are defined in Appendix 5. A treatment-emergent PCSV is any PCSV which developed or worsened in severity compared to baseline during the treatment and/or follow-up period. The time interval to detect any event or abnormality is between the first injection of study medication and EOS.

In addition, the summary of safety results (including TEAEs, clinical laboratory, vital signs and ECG) will be performed for subjects who were impacted by COVID-19 pandemic and not impacted by COVID-19 pandemic in each study part, respectively if deemed appropriate. The summary will be performed for pre-, during, and post-COVID-19 periods for patients impacted by COVID-19, if deemed appropriate.

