### **5.7.3. Analysis of Vital Signs**

Summaries of vital sign variables will include:

- Descriptive statistics of vital sign variable and change from baseline by visit
- The number (n) and percentage (%) of patients with treatment-emergent PCSV
- Shift tables based on baseline normal/abnormal and other tabular and graphical methods may be used to present the results for parameters of interest

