**Table 4: Analysis Visit Window for Safety labs, Vitals, PK and Biomarkers**

Visit from SOE	Target Study Day in Part B a	Vital signs	Physical examination, ECG, Height, Weight	Lab*	PK, ADA	TARC#, Serum Immunoglobulin profiling, antigen-specific IgE
Baseline	1	≤1	≤1	≤1	≤1	≤1
Week 1	8	[2, 11]				
Week 2	15	[12, 22]				
Week 4	29	[23, 43]		[2, 71]	[2, 43]	[2, 71] #
Week 8	57	[44, 71]			[44, 71]	
Week 12	85	[72, 99]			[72, 99]	
Week 16	113	[100, 127]	[2, 155]	[72, 155]	[100, 127]	[72, 155]# [2, 155]
Week 20	141	[128, 155]			[128, 169]	
Week 24	169	[156, 183]				
Week 28	197	>= 184	>= 156	>=156	>= 170	>= 156

\*Hematology and Blood Chemistry only.

#Only for TARC which was collected at baseline, Day 29, Day 113/EOT and Day 197/EOS.

Note that both scheduled and unscheduled measurements will be considered for determining abnormal/PCSV values for laboratory, vital signs or ECGs as well as the baseline values.

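### The date-only baseline rule in SAP 6.1 cannot pick out the Day 1 pre-dose vital signs that the plan itself requires

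*SAP*

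**What the plan says.** The lead sentence of SAP 6.1 sets baseline, unless specified otherwise, at the last valid value before study drug is first given. Protocol 9.6 agrees: "The baseline assessment in part B will be the latest valid, pre-first-dose assessment available in part B".

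SAP 6.1 then gives two rules for applying this. Rule 1 compares both date and time with the first injection, for AE, laboratory, PK and ADA data. Rule 2 covers everything else: "For other data except AE, lab, PK or ADA, only date of the measurement will be used to determine baseline". Vital signs are not in rule 1, so rule 2 governs them.

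On the schedule, protocol 6.2.3.1 says vital signs "will be collected pre-dose at every in-clinic visit". SAP 4.5.3 adds readings after dosing: "Vital signs (systolic and diastolic blood pressure, heart rate, respiration, and temperature) will be performed at 30 minutes" and again at 2 hours. Protocol 5.1 and the footnotes to the schedule of events apply this to the first three doses, and Day 1 is the first of them.

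On use, SAP 5.7.3 plans "Descriptive statistics of vital sign variable and change from baseline by visit", treatment-emergent PCSV counts and possibly shift tables. SAP 5.7 states: "The time interval to detect any event or abnormality is between the first injection of study medication and EOS".

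**The concern.** Rule 2 is meant to carry out the pre-dose definition, but the information it allows cannot separate a pre-dose reading from a post-dose reading taken the same day. Vital signs are the only rule 2 variable with scheduled post-dose readings on the day of first dosing, so the gap matters only for them.

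In Appendix 5 of the SAP, the PCSV criteria for heart rate, systolic and diastolic pressure and respiratory rate all depend on the baseline value. If a post-dose reading becomes the baseline, a change caused by the first injection becomes the reference. It can then hide PCSVs on Day 1 and at later visits, and it distorts every later change from baseline. The readings at risk come from the 2-hour observation that the protocol (1.2.3.2) includes to detect immediate hypersensitivity.

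**Working it through.** **Step 1. Apply rule 2 to Day 1.** The three scheduled sets (pre-dose, 30 minutes, 2 hours) carry the same date, the first injection date. Rule 2 does not say whether that date qualifies.

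- *Reading 1: the injection date qualifies.* All three sets are eligible and date alone cannot rank them. If the latest is then taken, as the lead sentence asks, the 2-hour post-dose reading is chosen. This is the likelier reading, because rule 2 also governs IGA and EASI, whose baselines are assessed on Day 1. SAP 2.1 says: "Patients who continue to meet eligibility criteria at baseline undergo day 1/baseline assessments".
- *Reading 2: the injection date does not qualify.* All three sets drop out. The only earlier scheduled vital signs are at Visit 1 (day -56 to -15), since none are scheduled at Visit 2. Baseline is then at least 15 days old and the Day 1 pre-dose reading counts as post-baseline.

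Neither reading returns the Day 1 pre-dose value.

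**Step 2. Look for a tie-break elsewhere.**

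- The first-observation rule in protocol 9.6 is for laboratory values.
- The same-day rule in SAP 6.4 is for unscheduled visits.
- The note under SAP Table 4 says "both scheduled and unscheduled measurements will be considered for determining abnormal/PCSV values for laboratory, vital signs or ECGs as well as the baseline values", which excludes no post-dose reading.
- The Table 4 windows do not help, because SAP 6.4 does not apply them to scheduled visits.

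**Step 3. Consequences of a 2-hour baseline, from the Appendix 5 criteria alone.**

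- The 2-hour reading has change 0 from itself. It can never meet the 20 bpm, 20 mmHg systolic or 10 mmHg diastolic change condition.
- If heart rate is still r bpm above pre-dose at 2 hours, the later change condition moves from +20 to +(20 + r) over pre-dose. Illustration with assumed values, age 1 to under 3 years (criterion: at least 140 bpm and a rise of at least 20): pre-dose 118, 2-hour 128, week 4 140. Against pre-dose, 140 − 118 = +22, which is flagged. Against 2 hours, 140 − 128 = +12, which is not.
- The high respiratory-rate criterion requires baseline at or below 34 per minute (1 to under 6 years) or 40 (under 1 year). A child above that limit at 2 hours cannot be flagged high at any later visit.

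**Step 4. Size under stated assumptions.** The documents give no vital-sign distributions, so the inputs below are assumed and varied. They describe children aged 3 to under 6 years whose heart rate rises after dose 1.

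- Mean heart rate 100, 110 or 120 bpm; rise at 30 minutes 20, 35 or 50 bpm; share of the rise left at 2 hours 0, 0.5 or 1.
- Between-child SD 10 and within-child SD 8.
- Criterion: at least 140 bpm and at least +20 from baseline.
- 3 × 3 × 3 = 27 scenarios, 200,000 simulated children each.

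Proportion flagged on Day 1 at either post-dose reading, minimum to maximum over scenarios:

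| Share of rise left at 2 hours | Pre-dose baseline | 2-hour baseline |
|---|---|---|
| 1.0 | 8.5–99.8% | 1.0–3.9% |
| 0.5 | 5.3–98.8% | 3.0–67.0% |
| 0 | 4.9–98.7% | 4.9–98.7% |

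The 3.9% ceiling can be checked by hand. With full persistence, the 30-minute minus 2-hour difference has mean 0 and SD 8 × √2 = 11.3. The chance that it reaches 20 is P(Z ≥ 20/11.3 = 1.77), about 0.038. With a screening baseline, the flag rates agreed with the pre-dose baseline to within 0.001.

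**Step 5. Mean change from baseline.** In an affected child, later change is shifted by −(share × rise), from 0 to −50 bpm. Over all children the shift is −(prevalence × share × rise). With an assumed prevalence of 1–10%, the extreme is −(0.10 × 1 × 50) = −5.0 bpm.

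**The case against.** The best defence is that this is an unresolved tie and not a rule that selects a post-dose value. Ranking same-date readings needs clock time, which rule 2 excludes. The lead sentence of SAP 6.1 and protocol 9.6 both require a pre-dose value, and SAP 5.7 treats everything after the first injection as on treatment, so the intent is clear and a sensible programmer would use the pre-dose record. The fallback to screening loses no flags in the simulation. The percentages rest on assumed inputs, with a rise set at or above the criterion itself. Vital signs are only summarised descriptively, both arms are treated alike, and adverse events are assessed at the same post-dose times.

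Much of this stands. Intent is clear, the size is not known from the documents, and the reach is limited. But clear intent does not repair the rule. An analyst can reach the intended value only by using time or a timepoint label, which rule 2 rules out. Rule 1 shows that the authors used time for other data types. That the stated rule contradicts the definition it serves does not depend on any assumed number.

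**Conclusion.** The concern holds: rule 2 is wrong as written for vital signs. It should be corrected, but it does not threaten the trial's main conclusions.

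The effect is confined to vital-sign change from baseline, shift tables and the PCSVs with a baseline condition. The temperature PCSV has none, reactions reported as AEs or AESIs are kept, and no efficacy analysis changes.

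Loss of flags arises under reading 1, and only when a change is still present at 2 hours. It can then be nearly complete on Day 1 for affected children. It is nil if the change has resolved or if screening serves as baseline, although a screening baseline is still not the value the plan requires. Confidence is high in the contradiction. The magnitudes are conditional on the assumed heart-rate values.

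**What to change.** In SAP 6.1, either move vital signs into rule 1, so that date and time are compared with the first injection, or define vital-sign baseline as the planned Day 1 pre-dose timepoint. Exactly one of the three scheduled Day 1 sets then qualifies. State also that the Day 1 30-minute and 2-hour readings are post-baseline for PCSVs and change from baseline, in line with SAP 5.7.

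The cost is about one sentence of SAP text. No new data should be needed, because the post-dose readings already have timed windows (30 ± 10 minutes and 2 hours ± 15 minutes).

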### 6.2. General Data Handling Conventions

For the laboratory safety variables data, if the data fall below the lower limit of quantification (LLOQ) / limit of linearity, half of the lower limit value (i.e., LLOQ/2) will be used for quantitative analyses. For data above the upper limit of quantification (ULOQ) / limit of linearity, the upper limit value (i.e., ULOQ) will be used for quantitative analyses.

### 6.3. Data Handling Convention Missing Data

Missing data will not be imputed in the listings. This section includes the methods for missing data imputation for some summary analyses, if necessary.

#### *Adverse event*

If the intensity of a TEAE is missing, it will be classified as “severe” in the frequency tables by intensity of TEAE. If the assessment of relationship of a TEAE to the investigational product is missing, it will be classified as “related” in the frequency tables by relation to the investigational product.

#### Adverse event start date

AE start date will be used for AE classification and analysis of AESIs. If AE start date is not complete, then the character variable will keep the original incomplete date, the numerical date variable will be imputed, and an imputation flag will indicate which date component is missing.

If AE start day is missing, and AE start month and year are not missing: If AE start year is the same as first dose year and the AE start month is the same as the first dose month then impute AE start day using the day of first dose. If this leads to a date after the AE end date, use the AE end date instead. Otherwise impute the AE start day using the first day of the month. If this leads to a date before informed consent, the informed consent date will be used. Imputation flag is ‘D’.

If AE start month is missing, and AE start year is not missing: If AE start year is less than the first dose year, use the informed consent day and month. If AE start year is equal to the first dose year, use the first dose day and month. If this leads to a date after the AE end date, use AE end date instead. If AE start year is after the first dose year, use 01 January. Imputation flag is 'M'.

If AE start year is missing: Impute AE start date using the day of first dose. If this leads to a date after the AE end date, use AE end date instead. Imputation flag is 'Y'.

#### **Adverse event end date**

The general recommendation is not to impute AE end date. However, since AE end date will be used for AE starting date imputation, in order to carry through the logic for programming, the following intermediate step will be used. Afterwards, only the original character/numeric date recorded in CRF will be kept in the final analysis dataset.

If AE end day is missing, and AE end month and year are not missing: Impute AE end date using the last day of the month. If this leads to a date after end of study follow up date, use end of follow up date instead.

If AE end month is missing, and AE end year is not missing: Impute AE end date using 31 December as the day and month. If this leads to a date after end of study follow up date, use the end of follow up date instead.

If AE end year is missing: Impute AE end date using the end of follow up date.

#### ***Medication start and end date missing***

To determine whether a medication is pre-treatment medication or concomitant medication or both, the missing medication start date is estimated as early as possible, and the missing medication end date is estimated as late as possible. If the medication start date is missing, the onset day will not be calculated in medication listings.

#### **Prior medication start date**

If start day is missing, and start month and year are not missing: Impute the start day using the first day of the month. Imputation flag is 'D';

If start month is missing, and start year is not missing: Impute the day and month using 01 January. Imputation flag is 'M'.

If start year is missing: Impute start date using 2 years before informed consent date. Imputation flag is 'Y'.

A special note: for start date with year missing, the general principle is not to impute. However, in order to simplify the programming flow, the imputation is proposed in line with the protocol which specifies to collect up to 2 years of prior medication. Since the start date of prior medication will not be used in any analysis, the rule will not impact the analysis result.

#### **Prior medication end date**

If end day is missing, and end month and year are not missing: Impute end date using the last day of the month. If this leads to a date on or after first dose intake date, use first dose intake date - 1 instead. Imputation flag is 'D'.

If end month is missing, and end year is not missing: Impute end date using 31 December as the day and month. If this leads to a date on or after first dose intake date, use first dose intake date - 1 instead. Imputation flag is 'M'

If end year is missing: Impute end date using the first dose intake date -1. Imputation flag is 'Y'.

#### **Concomitant medication start date**

The imputation rule for concomitant medication start date is the same as AE start date.

#### **Concomitant medication end date**

If end day is missing, and end month and year are not missing: Impute end date using the last day of the month. If this leads to a date after end of study follow up date, use end of follow up date instead. Imputation flag is 'D'.

If end month is missing, and end year is not missing: Impute end date using 31 December as the day and month. If this leads to a date after end of study follow up date, use the end of follow up date instead. Imputation flag is 'M'.

If end year is missing: Impute date using the end of follow up date. Imputation flag is 'Y'.

#### **Medication coding**

Medications whose ATC level 4 cannot be coded will be summarized by setting ATC4=ATC2 in the table programs. However, these uncoded ATC level 4 records still need to be confirmed with study DM and study MD.

#### **PCSV**

Patients who had a post-baseline PCSV but a missing baseline value will be regarded as having a treatment emergent PCSV.

### **6.4. Analysis Visit Window**

Data analyzed by-visit-analysis (including efficacy, laboratory data, visit sign, ECG, ADA) will be summarized by the study scheduled visits described in the study protocol and SAP "Schedule of Events". The analysis visit windows will be exhaustive so that all available values obtained from unscheduled visits, early termination (ET) visit have the potential to be summarized. No analysis visit windows will be applied for the study scheduled visits.

The analysis visit windows are created per study Schedule of Events (SOE) table for each parameter and will be applied if the data from study scheduled visits are unavailable. The following general rules will be applied to unscheduled visit and/or early termination (ET) visit mapping for each parameter.

1. If ET visit falls in an analysis window which already has no missing observed value of this parameter from the scheduled visit, ET will be mapped to the next scheduled visit.
2. If both ET visit and unscheduled visit of the same parameter are available in the same analysis visit window, only ET visit will be mapped.
3. If multiple unscheduled visits of the same parameter are available in the same analysis visit window, the unscheduled visits will be mapped using the following rules:

- a. The closest unscheduled visit from the target day will be selected.
- b. If multiple unscheduled visits exist on the same day, the first unscheduled visit will be used.

4. If mapping distance is greater than 2 weeks, the unscheduled visit will not be mapped.

Unscheduled visits and early termination (ET) visit will be mapped per the following analysis visit windows based on the visit schedule of each parameter as per [Appendix 3](#).

